The study will use a cluster randomized controlled trial design. A sampling frame of villages in Wajir County that meet the following inclusion criteria will be constructed: a) have a functioning community health unit, b) have more male students enrolled in upper primary school levels (Classes 6, 7 and 8) as compared to girls, c) have at least one female teacher in the primary school and d) have a functioning school feeding program. Urban and peri-urban areas will be excluded. Ten villages, stratified by sub-county and village size will be randomized assigned to each study arm (see below for intervention components in each arm) for a total of 30 villages. The randomization will take place publicly with eligible village leaders in attendance to increase acceptance of the randomization results. Do to the vast geographical nature of Wajir County, the villages are quite far from one another, therefore there is little risk of contamination between study villages.

Geographical Setting

The study will take place in Wajir County, located in the mainly rural, semi-arid region of Northern Kenya, and inhabited by a mainly pastoralist, Muslim population of Somali origin. Less than a quarter of adults in Wajir are literate, half of women 20-24 were married by age 18 and the total fertility rate is 7.8 (over double the national average of 3.6) ²⁸. Girls' education outcomes are incredibly poor relative to national levels with two-thirds of girls ages 6-17 having never been to school ²⁹.

5. Intervention

There are three intervention components being tested: a) community conversation groups, b) girls' safe spaces groups and c) monetary/material incentives conditioned on school enrollment. All schools will also have a pre-existing school feeding program in place. The main target are girls ages 11-14 years old. The intervention will start at the end of April 2022 with the start of the 2022 school year and end in March 2023 during the first term of the 2023 school year.

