Cash: All payments will be conditioned on girls being enrolled in school. Enrollment will be verified during the second month of each term and payments made by the end of that month. Household heads that had an out of school girl ages 11-14 at the start of the intervention period will receive a one-time payment of 4500/ (~US\$ 41). In addition, household heads of all girls 11-14, regardless of baseline school status, will receive 1500/ (~\$13.50) each term thereafter (total of four payments). Cash transfers will be paid via Mpesa to the household head determined at the time of registration. If the household has more than one girl between the ages of 11-14, they will all be eligible for their own cash transfer.

In-Kind: Girls who are out of school at baseline will receive an in-kind incentive if they enroll in school during the first term of the 2022 school year. All girls still enrolled in school during the first term of the 2023 school year will receive another incentive. The exact incentive (e.g. a goat or a school supply kit) will be determined during the formative assessment to take place in Q1 2022. In addition, a community level enrollment target will be set at 10 percentage points above baseline enrollment. If the community meets the enrollment target at the end of the program, an in-kind project will be given that values approximately US\$5000 (e.g. building classrooms or latrines at the school) which will be implemented and monitored by the community conversation group members.

The arms are as follows:

6. Study Goals/Objectives

The overall objective of this study is to determine which modified version of the original AGI-K intervention model is optimized for scale up based on effect, feasibility and cost of delivery via government channels.

The study involves the evaluation of three different packages of interventions to enrol and retain out of school girls aged 11-14 and change social norms related to girls' education and child marriage, in Wajir. All three packages will include girls' empowerment groups and community engagement on gender attitudes, layered on top of existing school feeding programmes, plus:

- 1) In some communities, no additional incentive
- 2) In some communities, an in-kind incentive for the whole community for school enrolment and retention, as well as an in kind incentive for individual girls

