8. Data Collection Activity 3: Baseline Survey

a. Sub	ject Population
	The study population is girls between the ages of 11 to 14 residing in the 30 selected study villages in Wajir. The participants for the baseline survey will be approximately 1,500 girls between aged 11 to 14 (~500 per arm). In addition, in each household, the parent/guardian who provides consent for the girl to participate in the survey will also participate in a short interview on the household characteristics (1,500 parents/guardians in Wajir).
	All girls between the ages of 11 and 14 during the time of the survey, residing in study villages will be listed from the household listing above and households will be randomly selected for the baseline interview. In households with more than one eligible girl, only one will be interviewed.
	All eligible girls who consent to the interview will be interviewed at baseline. Once the survey is complete, villages will be randomly assigned to study arms during a public lottery. Once randomization is completed, girls, households and community members will be invited to participate in the various components of the programmes, based on their assigned study arms. Mentors and other programme staff will visit the girl in her home and discuss the benefits of the programme with both the girl and her parent/guardian. They will then invite the girl to participate in the programme, obtain the necessary consents and follow-up with the girl to ensure that she has enrolled in programme activities.
b. Res	earch Protocol
	The baseline survey will be conducted between March and April 2022, before intervention activities take place. This period was chosen so that the intervention can start at the end of April which is the start of the 2022 school year (delayed because of COVID-19).
	Due to the sparse geography in Wajir, the research team will arrive in a village and use 1-2 days to complete the household listing. Immediately following they will spend the next 2-5 days completing the baseline survey.
	Trained interviewers will be grouped into teams of 5-8, each team with a supervisor to provide directly quality assurance at the time and location of interviewing. The data

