the household. b. Research Protocol ☐ School enrolment data will be verified three times throughout the life of the study – once per school term for the 2022 school year. ☐ School enrolment data will be used for two key purposes: 1) to determine eligibility for cash transfers and in-kind incentives and 2) track overall levels of school enrolment among 5-14 year olds in the study villages. ☐ Data collectors will visit the school administrator once per term with the enrolment register and confirm which students are enrolled. c. Risks and Benefits to Subjects RISKS ☐ The collection of monitoring data will not increase risk for girls or boys because their anonymity will be maintained using a unique ID, and no identifying information will be included in data provided by the financial institution. ☐ There is a minor risk of loss of privacy due to the collection of contact information for tracking purposes. **BENEFITS** ☐ There is no direct benefit to the school administrators. d. Steps to Minimize Risks ☐ To minimize the risk of loss of privacy, data will be collected using electronic data capture and will be stored on password-protected computers at the Population Council office. e. Confidentiality ☐ Steps to ensure confidentiality of monitoring data are the same as those described for the monitoring data above. f. Compensation ☐ The participants will not be paid for the collection of monitoring data. g. Informed Consent Process ☐ After the completion of the baseline survey and randomization to study arms, girls and

their parents/guardians will be invited to participate in the program and informed about

younger school aged children to be able to assess effects on enrolment of all children in

the intervention activities and the types of monitoring data that will be collected as part of the intervention. Both parents/guardians and girls will be asked to sign consent/assent forms for program participation, that includes collection of monitoring data as described above. A separate form will be developed for each arm to describe the interventions/monitoring activities unique to each arm (i.e. education attendance, group attendance and account transactions).

9. Data Management

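### No school-register reading precedes the lottery or falls at programme end, so the register series has no same-source baseline and the community target no same-source reading at either end

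*Protocol*

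**What the plan says.** **Register readings.** Activity 7 (School Enrollment Data, b) plans: "School enrolment data will be verified three times throughout the life of the study – once per school term for the 2022 school year". The Overview Table (section 7) gives May, August and October 2022. The readings serve two purposes: "to determine eligibility for cash transfers and in-kind incentives" and to "track overall levels of school enrolment among 5-14 year olds in the study villages". The children to be checked come from the household listing.

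**Community target.** In the in-kind arm, section 5 states that "a community level enrollment target will be set at 10 percentage points above baseline enrollment". It is judged when the programme ends, and a village that meets it receives a project worth about US$5000. No source, age/sex group or date is given for the baseline. The same paragraph rewards out-of-school girls who enrol in the first term of 2022, and girls still enrolled in the first term of 2023.

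**Timing.** Section 5: "The intervention will start at the end of April 2022 with the start of the 2022 school year and end in March 2023". Activity 3: "The baseline survey will be conducted between March and April 2022, before intervention activities take place". On allocation, Activity 3 adds: "Once the survey is complete, villages will be randomly assigned to study arms during a public lottery".

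**The concern.** A target defined as a rise from baseline needs the same measurement at both ends. As scheduled, the register supplies neither. The first reading comes after villages know their arm, within the term whose enrolment earns the first individual in-kind incentive. The last comes in October 2022, five months before the programme ends.

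Two things are at stake. One is the trigger for the community project, which bears on what the in-kind package delivers and costs, and cost is one of the four study questions in section 6. The other is the register series on children aged 5-14. It has no pre-allocation value from its own source, either for describing change or as a village covariate in a trial with 10 villages per arm. This is a matter of data collection and of an incentive rule, both fixed in the protocol. No analysis plan can adjust for a reading that was not taken.

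**Working it through.** **1. Order of events**

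| Event | Date | Place in protocol |
|---|---|---|
| Household listing, baseline survey | March-April 2022 | Activities 2 and 3 |
| Public lottery | once the survey is complete | Activity 3 |
| Programme start | end of April 2022 | Section 5 |
| Register readings | May, August, October 2022 | Overview Table; Activity 7 |
| Programme end, target judged | March 2023 | Section 5 |
| Endline survey | April-May 2023 | Activity 4 |

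Register readings before the lottery or start: 0 of 3. Register readings in 2023: 0 of 3.

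**2. What could serve as baseline enrolment**

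- *May 2022 register*: same source as the later readings, but after the lottery and the offer.
- *Household listing*: before the lottery, but an adult's report, with rosters completed only where a girl aged 10-15 lives. The text describes no enrolment item. The form (Annex 2) is not shown and may contain one.
- *Baseline survey*: before the lottery, but interviews with about 50 sampled girls aged 11-14 per village.
- *Village selection data*: the inclusion criterion compares boys and girls in Classes 6-8. It gives no enrolment rate among listed children.

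None is at once register-based, before the lottery and on the register series' population.

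**3. Effect on the 10-point target** (the shifts and gaps are assumptions)

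*May as baseline.* Let p be true pre-lottery enrolment and s the early response already present in May. Target = p + s + 10, so the true rise required is 10 + s. With p = 75%, the earlier trial's Wajir figure quoted in Background:

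| s (points) | Target | True rise required |
|---|---|---|
| 0 | 85% | 10 |
| 5 | 90% | 15 |
| 10 | 95% | 20 |

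With p = 85% and s = 10 the target would be 105%, which cannot be met.

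*Household report as baseline, register at the end.* Let d be register minus report. The true rise required is 10 - d: with d = -5 it is 15 points, with d = +5 it is 5 points.

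*As a share of out-of-school girls.* At 75% enrolled: 10/25 = 40%, with 5/25 = 20% and 15/25 = 60% under the assumed gaps. Geographical Setting says that two-thirds of girls aged 6-17 have never been to school, so at most about a third are enrolled. On that figure the shares are about 10/67 = 15%, 5/67 = 7% and 15/67 = 22%. The shift in points is the same, but its practical weight depends strongly on the starting level. Section 5 also does not say that the target counts girls only.

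The precision gained from a same-source village covariate cannot be computed, because the protocol gives no between-village variance or correlation over time.

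**The case against.** A reader might infer that the trial has no enrolment baseline, or that its enrolment comparison is biased. The documents do not support either reading. Villages are randomised, so comparing later register enrolment between arms is valid without a baseline. The baseline and endline surveys interview the same girls by the same procedures and cover schooling, so enrolment among out-of-school girls can be measured as a matched pair for the sampled 11-14 year olds. Those points stand. They do not reach the register series on 5-14 year olds, or the target.

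A reader might also infer that the target decides whether the in-kind package is delivered. It governs only the community project; the individual incentives do not depend on it. Nor does May follow the first cash payment: section 5 has verification precede payment, so May follows the offer and may, rather than must, contain a response to it.

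It is tempting to add that a baseline from 50 surveyed girls has a 95% margin of about ±12 points (1.96 × √(0.75 × 0.25/50)), wider than the target itself. This should carry little weight. Out-of-school status must be known for every eligible girl, so the listing is the likelier source, and the margin ignores any finite-population correction.

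Two further objections stand in part. A past term's register could be read at the May visit, so the schedule does not make the information irrecoverable; but the protocol does not plan this. And a pre-2022 register belongs to the previous school year, so change from it includes the year-to-year transition. That does not harm its use as a covariate, but it should be acknowledged when the target is defined.

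**Conclusion.** The point holds as a gap in the measurement schedule that should be closed. It is not a flaw in the randomised comparison. On the protocol's own dates, the register series has no same-source value before allocation, and the community target has no same-source reading at either end. The direction of the problem depends on what is taken as baseline: an early response in May would raise the bar, and a gap between report and register could move it either way. The 5 to 20 point range for the true rise required rests on assumed shifts of 5 to 10 points and assumed gaps of 5 points, which nothing in the protocol confirms or excludes. The missing 2023 reading needs no assumption. Section 5 makes both the community project and the second individual in-kind incentive depend on enrolment in early 2023, Activity 7 says that the register determines eligibility for in-kind incentives, and the schedule stops in October 2022. These passages must be reconciled.

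**What to change.** 1. During the listing and baseline visit, check listed children against the school's register for the last term before the 2022 school year. If that is not possible, take it retrospectively from the same school records. The pre-lottery visit is preferable because the school does not yet know its arm.
2. State in section 5 and Activity 7 that baseline and final enrolment for the community target use this one source and the same age/sex group, and name the dates.
3. Reconcile section 5, the Overview Table and Activity 7 so that a matching register reading is scheduled at programme end, in the first term of 2023.
4. Use the pre-lottery village value as a covariate when register enrolment is compared between arms.

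The cost is some extra field time per village, one further register round, and school permission sought earlier. Teams already spend 3 to 7 days in each village (1-2 for the listing, 2-5 for the survey). The workload is not trivial: about 15,000 households over 30 villages is roughly 500 to be screened per village, although only those with a girl aged 10-15 contribute children to check.

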	Participants will have the opportunity to experience mainly indirect benefits from the study, in the sense that the information they are providing will directly inform the development of scalable interventions to improve the lives of adolescent girls. Participants in Wajir and in intervention sites in Nairobi will directly benefit through the interventions that will be implemented in their communities or that they will participate directly based on their assigned study arm.
d. Ste	ps to Minimize Risks
	To minimize the risk of loss of privacy, data will be collected using biometrics and mobile phones or electronic data capture and will be stored on password-protected computers at the Population Council office. In addition, no identifying information will be included in the data provided by the financial institution.
e. Con	e fidentiality
	Steps to ensure confidentiality of monitoring data are the same as those described for the Baseline Survey, above.
f. Con	npensation
	The participants will not be paid for the collection of monitoring data.
g. Info	ormed Consent Process
	After the completion of the baseline survey and randomization to study arms, girls and their parents/guardians will be invited to participate in the program and informed about the intervention activities and the types of monitoring data that will be collected as part of the intervention. Both parents/guardians and girls will be asked to sign consent/assent forms for program participation, that includes collection of monitoring data as described above. A separate form will be developed for each arm to describe the interventions/monitoring activities unique to each arm (i.e. education attendance, group attendance and account transactions).
8. Dat	a Collection Activity 7: School Enrollment Data
a. Sub	ject Population
	The study population is all girls and boys 5-14 years old residing in the 30 study villages. This list will be derived from the household listing (see above). We are including

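### Consent for school-register data is placed after the public lottery on arm-specific programme forms, in conflict with the overview table and the stated population; if followed, register outcomes may be ascertained differently by arm

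*Protocol*

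**What the plan says.** Section 8, Activity 3 (a) fixes the order of events: "Once the survey is complete, villages will be randomly assigned to study arms during a public lottery". The household listing comes immediately before the baseline survey in each village (Activity 3, b), so it too precedes the lottery.

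Activity 7 (a) defines whose enrolment is tracked: "The study population is all girls and boys 5-14 years old residing in the 30 study villages". The list of children comes from the household listing. Status is confirmed with the school administrator once per term of the 2022 school year (Activity 7, b).

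Activity 7 (g) then sets the consent process. It opens "After the completion of the baseline survey and randomization to study arms, girls and" their parents or guardians are invited to join. It continues: "Both parents/guardians and girls will be asked to sign consent/assent forms for program participation, that includes collection of monitoring data as described above". It adds: "A separate form will be developed for each arm to describe the interventions/monitoring activities unique to each arm", and gives education attendance as one example of what is monitored. Activity 6 (g), for monitoring data, has nearly the same text.

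The Overview Table (section 7) gives the sample for School Enrollment Data as all girls and boys 5-14 and the study population as school administrators. It enters N/A for the informed consent document.

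**The concern.** In a cluster trial, consent taken once families know their arm is a familiar route to selection after randomisation. Here the form that would permit register data is also the form for joining the programme, and joining brings different things in different arms. Section 6 describes one arm with no additional incentive, one with goods for girls and the community, and one with cash for households. The reason to sign is therefore unequal by design.

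The outcomes exposed are those that lean on the register: the proportion of enrolled girls retained each term (section 6) and enrolment levels among all 5-14 year olds (Activity 7, b). The trial is meant to choose a package for scale-up, so an arm-related distortion of a few points in these measures would matter. Children missing in this way cannot be fully recovered by adjustment in the analysis.

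**Working it through.** The protocol states no consent rate and no figure to reproduce for this point. The check sets the passages side by side and then sizes the bias under stated assumptions.

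**1. Do the passages agree?**
- Population: all children 5-14 of both sexes (Activity 7, a; Overview Table). Signatories in Activity 7 (g): girls and their parents or guardians. Boys are not mentioned.
- Consent: N/A in the Overview Table; signed forms in Activity 7 (g).
- The N/A entry cannot settle the matter. The table has the same entry for Monitoring Data, although Activity 6 (g) asks for signed forms there.
- The listing has its own verbal consent (Activity 2, g), taken before the lottery. The Activity 2 text describes its uses as identifying eligible girls, supporting recruitment, and comparing households whose girls joined with those whose girls did not. It does not mention register follow-up. The roster is completed only where a girl aged 10-15 lives (Activity 2, b), so the listing does not by itself reach every child aged 5-14.
- No passage says whether children of families who do not sign stay in the register check.

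**2. How large could the bias be if signing gates the data?**

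Inputs:
- p, true enrolment in both arms: 75%, borrowed from the Wajir baseline of the earlier trial (section 4). Using it here is an assumption.
- Signing in an incentive arm: 95% whatever the enrolment status (assumption). Observed enrolment there stays at 75%.
- c_e and c_o, signing among enrolled and out-of-school girls in the no-incentive arm: assumptions, varied below.

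Observed enrolment among signers = p·c_e / [p·c_e + (1 − p)·c_o].

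| c_e / c_o | Calculation | Observed | Excess over 75% |
|---|---|---|---|
| 90% / 90% | 0.675 / (0.675 + 0.225) | 75.0% | 0.0 points |
| 90% / 80% | 0.675 / (0.675 + 0.200) | 77.1% | 2.1 points |
| 95% / 80% | 0.7125 / (0.7125 + 0.200) | 78.1% | 3.1 points |
| 90% / 70% | 0.675 / (0.675 + 0.175) | 79.4% | 4.4 points |
| 95% / 70% | 0.7125 / (0.7125 + 0.175) | 80.3% | 5.3 points |
| 90% / 60% | 0.675 / (0.675 + 0.150) | 81.8% | 6.8 points |
| 90% / 50% | 0.675 / (0.675 + 0.125) | 84.4% | 9.4 points |

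The first row shows that a lower signing rate alone does no harm. What matters is how signing relates to enrolment within an arm. With no true difference, the no-incentive arm looks better by the amount in the last column, so a real incentive effect would be understated by roughly that much. If the selective signing were in an incentive arm instead, the direction would reverse. If every listed child is checked, the bias is zero.

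**The case against.** A reader might infer that who has outcome data does depend on the arm. The documents do not say so. Nothing states that children of non-signers are dropped. The stated population is everyone aged 5-14, status comes from the school administrator, and non-joiners are kept at least in the listing data. Activity 7 (g) may be text carried over from Activity 6: the two nearly match, and Activity 7's risk paragraph also refers to data from the financial institution, which has no bearing on school registers. If signing really gated the data, it is hard to see how boys and younger children would be covered at all, and covering them is a stated purpose. Carry-over is an inference, but a reasonable one.

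A reader might also infer that the register is the main outcome source. That is not stated either. The endline survey takes all baseline girls, whether or not they joined (Activity 4, a), and the girls' questionnaire covers schooling history (section 11). The register checks fall within 2022 only, so they cannot show transition to the next school year.

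Nor is it established that families in the no-incentive arm will sign less. Every arm offers girls' groups and community conversations, and staff visit homes to invite girls. The signing rates above are invented for illustration, and they concern overall enrolment, whereas the first outcome listed in section 6 is enrolment among girls who were out of school.

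Finally, consent pages are not in the copy reviewed, so the listing or baseline forms may already cover register linkage.

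All of this limits the point to a conditional one. It does not remove it. Activity 7 (g) is the only consent rule written for register data. The survey covers one girl aged 11-14 per selected household, so it leaves out boys and younger children and does not replace the termly checks.

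**Conclusion.** The conflict within the protocol is definite: Activity 7 (g) calls for signed, arm-specific, post-lottery consent from girls and parents, while the Overview Table says consent does not apply and Activity 7 (a) includes all children 5-14.

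The bias is conditional. It arises only if Activity 7 (g) is enforced as a condition for register data and signing relates to enrolment differently between arms. Under the assumed rates shown, with less signing among out-of-school girls in the no-incentive arm, that arm's enrolment is overstated by about 2 to 9 points and the incentive effect understated. The exposed measures are termly retention and all-child enrolment from the register. Girls' schooling measured at endline is not tied to joining. The documents do not support an unconditional statement that outcome data depend on arm, but they leave open a route to post-randomisation selection that is cheap to close.

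**What to change.** - Reconcile Activity 7 (a), Activity 7 (g) and the consent row of the Overview Table, so that the protocol says once whether register data need consent and from whom. Check the Monitoring Data entry in the same row against Activity 6 (g).
- Obtain any consent or assent needed for register linkage at the household listing or baseline survey, before the lottery, in one wording identical in all 30 villages and covering all listed children 5-14, boys included.
- Keep the arm-specific forms for programme participation only.
- State that register follow-up and analysis include every child listed before randomisation, whether or not the family joins.

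The cost is a consent paragraph and an ethics amendment. The listing consent is verbal and may need upgrading for this item. The change has to be in place before the lottery to be of use.
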